1. The first step is to understand the pattern of missingness. In order to perform the multiple imputation, a monotone missing pattern has to be achieved. For example, if there exist values for baseline and Week 8 visits, but missing values for the Week 2 or 4 visits, Markov-Chain Monte-Carlo (MCMC) method will be used to impute the small amount of missing data that may be missing at the intermediate visits that is required to make the missing data pattern monotone before applying the multiple imputation algorithm. This method uses a non-informative Jeffreys prior to derive the posterior mode from the expectation-maximization (EM) algorithm as the starting values for the MCMC method. MCMC method will use seed of 66447809. All the endpoints will be considered as continuous for this step. To avoid values that could not be observed in practice for S-IGA, B-IGA, total PSD score, and PSSI, imputed values will be constrained to be integers in the range of the observed endpoint. Since SI-NRS and WI-NRS scores will be calculated as average weekly scores and PASI is a derived score that can have non-integer results (see [Section 6.1.7](#) for more information), this restriction will not apply for those endpoints. Total of 10 imputations are done in the MCMC step.
2. Once the monotone pattern is achieved, the next step is to implement the imputation algorithm. For this, the Predictive Mean Matching method (PMM) will be used. This method is particularly helpful if the normality assumption is violated. For subjects with complete data up to a particular visit, a PMM model will be fit that includes the outcome at that visit as the dependent variable and as independent variables, the outcome at previous visits, pooled site, and treatment group using a seed of 90066927. This process will be repeated 15 times, resulting in a total of 150 complete analysis datasets. The seed may be changed after unblinding in case of any issues with the imputation process, and it will be documented in the CSR if any change is required.

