3. For each completed dataset, compute the necessary derived variables. The categorical endpoints will be analyzed using the CMH analysis for each of the complete analysis data sets stratified by pooled site group, baseline S-IGA category, and baseline B-IGA category. The results will be combined into one multiple imputation inference (odds ratio, associated CI, and *P* value) using PROC MIANALYZE as illustrated⁴. The continuous endpoints will be analyzed using descriptive summaries, and an ANCOVA for each of the complete analyses data sets with terms for the baseline outcome, pooled site group, baseline S-IGA category, and baseline B-IGA category as covariates. The descriptive summaries will use the averaged imputed outcomes across all datasets for each subject, and the ANCOVA results will be combined into one multiple imputation inference (LS means, standard errors [SEs], 95% CIs, 97.5% CIs, and *P* values) using PROC MIANALYZE as illustrated⁴.

This approach to imputation should be superior to other strategies such as carrying forward the last available observation, which may yield unrealistic imputed values. Also, the use of multiple

imputation avoids the problem of artificially increasing power through data imputation associated with single-imputation methods because it accounts for the uncertainty associated with the imputation. Other missing data will not be imputed, with the exception of incomplete dates as described in [Section 6.1.8](#). For responder analyses, missing data will be treated as a nonresponse with the exception of S-IGA and B-IGA. Only observed data will be summarized using descriptive statistics.

The SAS pseudo code for the multiple imputation process is listed below:

Step 1:

```
proc mi data=example seed=66447809 n impute=10 round=1 out=example_1;
  mcmc impute=monotone;
  var <baseline score> ..... <visit8 score>;
run;
```

Step 2:

```
proc mi data=example_1 seed=90066927 n impute=15 out=example_2;
  by <MCMC imputation>;
  class <treatment> <pooled site>;
  monotone regpmm(<baseline score> ..... <visit8 score>);
  var <treatment> <pooled site> <baseline score> ..... <visit8 score>;
run;
```

Step 3:

- For categorical outcomes, this step involves running a CMH test stratified by pooled site group, baseline S-IGA randomization strata, and baseline B-IGA randomization strata on each completed dataset and combining the results using PROC MIANALYZE.

```
proc freq data=example noprint;
  by <imputationnumber> <visit> ;

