6.1.7. Derived Variables

Efficacy variable derivations described in this section will be performed with one exception. The exception is that subjects who discontinued early from study due to an AE or lack of efficacy will be considered as not having response (for MI and non-responder imputation analyses) and will be excluded from observed case analyses for all pre-specified analysis visits (refer to Section

6.1.5) on or after the associated analysis visit of the subject's last dose day). More specifically, for MI and non-responder imputation analyses, these subjects will be counted as non-responders for categorical variables and set to baseline for continuous variables for all visits on or after the associated analysis visit of the subject's last dose day.

- **Study day** is calculated as:
 - observation date – first dose date + 1, if record is collected on or after first dose date
 - observation date – first dose date, if record is collected prior to first dose date.
- **S-IGA Success** = S-IGA of “Clear” or “Almost Clear” plus at least 2-grade improvement from baseline.
- **B-IGA Success** = B-IGA of “Clear” or “Almost Clear” plus at least 2-grade improvement from baseline.
- **Average Weekly SI-NRS Score** = SI-NRS scores will be assigned to a particular study week based on the study week window, as shown in [Section 6.1.5.2](#). Average weekly baseline SI-NRS is derived as the average of all non-missing scores reported during the last 7 days prior to treatment if at least 4 of 7 evaluable daily SI-NRS questionnaires are available. Daily baseline SI-NRS is defined as the last non-missing assessment prior to the first study treatment.

If 2 or more observations are present for a single day, the most severe itch score will be used as a single daily value before calculating the average weekly score. The average of the reported (non-missing) SI-NRS scores assigned to each study week will be calculated. If at least 4 SI-NRS scores are present in this time period, the average weekly SI-NRS score will be calculated; otherwise, the average weekly score will be missing for that week. The derived average score will be rounded to 1 digit. Missing average weekly scores will be imputed as described in [Section 6.1.4.1](#).

- **SI-NRS Success** = achievement of at least 4-point reduction in average weekly SI-NRS score compared to baseline, calculated only for the subjects with SI-NRS ≥ 4 at baseline.

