8.2.6. Scalp Investigator Global Assessment (S-IGA)

The secondary efficacy endpoints relating to S-IGA score are:

- S-IGA score of “Clear” at Week 8
- S-IGA Success at Week 4
- S-IGA Success at Week 2

S-IGA Categorical Analysis

The estimand attributes (Section 8.1) can be described similarly to those described for the co-primary endpoints. This endpoint will be analyzed in the same manner as S-IGA (Section 8.1.1).

A summary of primary and secondary efficacy analyses is shown in Table 5.

Table 5: Summary of Primary and Secondary Efficacy Analyses

| Efficacy Endpoint | Primary Analysis | Sensitivity or Supplemental Analysis |
|--|--------------------------------|---|
| Primary ($\alpha = 0.025$) | | |
| S-IGA Success (IGA score of ‘0’ or ‘1’ plus at least 2-point improvement from baseline) at week 8 | ITT, multiple imputation (CMH) | #1 PP, observed data (CMH) #2 mITT, multiple imputation (CMH) #3 ITT, observed data (CMH) #4 ITT, non-responder imputation (CMH) #5 ITT, Tipping point #6 ITT based on different site pooling strategy #7 ITT without site stratification |
| B-IGA Success (IGA score of ‘0’ or ‘1’ plus at least 2-point improvement from baseline) at week 8 | ITT, multiple imputation (CMH) | #1 PP, observed data (CMH) #2 mITT, multiple imputation (CMH) #3 ITT, observed data (CMH) #4 ITT, non-responder imputation (CMH) #5 ITT, Tipping point #6 ITT based on different site pooling strategy #7 ITT without site stratification |
| Secondary Family 2 ($\alpha=0.005$) | | |

| | | |
|---|---|---|
| Family 1 ($\alpha=0.01$ or 0.015): Average weekly SI-NRS Success (achievement of at least a 4-point improvement) at Weeks 2, 4, 8 | SPRU4-ITT population, multiple imputation (CMH, odds ratio) | #1 SPRU4-ITT, observed data (CMH) #2 SPRU4-ITT, non-responder imputation (CMH) |
| Family 1 ($\alpha=0.01$ or 0.015): 
 • SI-NRS change from baseline at Week 1 • SI-NRS change from baseline at 72 hours • | ITT population, multiple imputation, ANCOVA | #1 ITT, observed data |
| Family 2 ($\alpha=0.005$): Average weekly WI-NRS Success (achievement of at least a 4-point improvement) at Week 8 | PRU4-ITT, multiple imputation (CMH) , odds ratio) | #1 ITT, observed data (CMH) #2 ITT, non-responder imputation (CMH) |
| Family 2 ($\alpha=0.005$): PASI-75 at Week 8 | ITT, multiple imputation (CMH) | #1 ITT, observed data (CMH) #2 ITT, non-responder imputation (CMH) |

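### Step 1 of the multiple imputation omits treatment, and 10 × 15 nested draws are pooled as 150 independent imputations: a small error that reaches several early alpha-controlled endpoints

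*SAP*

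**What the plan says.** SAP 6.1.4.1.1 sets out a three-step process.

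- **Step 1.** To make the missing-data pattern monotone, the "Markov-Chain Monte-Carlo (MCMC) method will be used to impute the small amount of missing data" at intermediate visits. The code is `mcmc impute=monotone` with 10 imputations and the list "var <baseline score> ..... <visit8 score>". Neither the prose nor the code mentions treatment.
- **Step 2.** Predictive mean matching takes the outcome at the visit as dependent variable "and as independent variables, the outcome at previous visits, pooled site, and treatment group". The code agrees: "var <treatment> <pooled site> <baseline score> ..... <visit8 score>". It runs BY the Step 1 draw, 15 times each, "resulting in a total of 150 complete analysis datasets".
- **Step 3.** CMH or ANCOVA is run on every dataset and the results are combined in one PROC MIANALYZE step. No nested combining rule is given.

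Section 6.1.4.1.2 uses a similar process for the supplemental estimand, and the tipping-point analysis (6.1.4.2) reuses Step 1. Table 5 makes multiple imputation the tested analysis for the secondary endpoints.

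The SAP is inconsistent on SI-NRS Success. Section 6.1.4.1.1 says: "For responder analyses, missing data will be treated as a nonresponse with the exception of S-IGA and B-IGA". Section 6.1.7 says: "Missing average weekly scores will be imputed as described in" Section 6.1.4.1, and Table 5 gives the analysis as "SPRU4-ITT population, multiple imputation (CMH, odds ratio)".

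**The concern.** An imputation model should contain the effect that the analysis will test. Step 1 models the scores pooled over arms, so a filled value depends on treatment only through the subject's other scores. Once filled, it is no longer missing and Step 2 cannot correct it.

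A value filled in Step 1 always has a later observed value, so Week 8 is never filled there. Family 2 and the co-primaries, all at Week 8, are touched only through Step 2 predictors. The exposed endpoints are:

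- Family 3: S-IGA Success at Weeks 2 and 4, and PASI change at Week 2.
- Family 1: SI-NRS change at Week 1, and SI-NRS Success at Weeks 2 and 4 if Table 5 governs.

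The Day 1 and 72-hour itch scores are daily values, and 6.1.4.1.1 lists only weekly averages for this process, so they are not included here.

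When effects are similar across visits, the early effect is diluted. When the effect grows over time it can be inflated, because Step 1 also conditions on later visits. Family 1 is tested in sequence and passes its alpha to Family 3 only if every test succeeds (6.1.3), so the Week 1 itch result also affects later tests.

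The pooling problem is distinct. For a subject with only intermittent gaps, the 15 datasets within a Step 1 draw are identical, yet they count as 15 separate imputations.

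**Working it through.** **Inputs.** From the documents: 10 × 15 = 150 datasets, as stated; about 280:140 subjects; S-IGA success of 46% and 11% at Week 8 (SAP 3.2, taking 46% as active because the arm labels appear transposed). Assumed: intermittent-gap rates of 5% and 10% (2% also run), correlations and time courses.

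**1. Mean scores, closed form (PASI change at Week 2).** Take effects δ in SD units, within-arm correlation matrix R and 2:1 allocation. The covariance that Step 1 sees is V = R + (2/3)(1/3)δδᵀ. The regression of Week 2 on baseline and Weeks 4 and 8 is β = Vₓₓ⁻¹Vₓᵧ, and the arm difference among filled values is βᵀδₓ.

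- Equal effects 0.5/0.5/0.5 at Weeks 2/4/8, exchangeable correlation 0.3: β = 0.171, 0.216, 0.216. Filled difference 0.216 × 0.5 + 0.216 × 0.5 = 0.216, a ratio to truth of 0.216/0.5 = 0.43. At 10% gaps the whole effect changes by 0.10 × (0.43 − 1) = −5.7%.
- Growing effects 0.2/0.5/1.0, correlation 0.7: β = 0.345, 0.284, 0.223. Filled difference 0.284 × 0.5 + 0.223 × 1.0 = 0.365, ratio 1.82. At 10% gaps the change is 0.10 × 0.82 = +8.2%.

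Over the scenarios run, the range is −7% to +8% at 10% gaps and −3% to +4% at 5%; a further set of scenarios reached −9% at 10%. With treatment in Step 1 this calculation recovers the true effect.

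**2. S-IGA Success.** Latent normal scores rounded to 0–4, N = 600,000 per scenario, 70 scenarios per visit. As written minus corrected, at 10% gaps: −1.4 to +0.2 points at Week 4 and −0.5 to +0.2 at Week 2, about half that at 5%. Other scenarios gave −1.0 to +0.3. At 2% gaps the shift is 0.0 to 0.2 points in size. In the largest Week 4 case z goes from 5.17 to 4.99.

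The full chain was also simulated at 280:140 with 10% gaps and 10% dropout. Bias in the success difference against full data, in percentage points:

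| Scenario | Visit | As written | Treatment in Step 1 |
|---|---|---|---|
| Early effect | Week 2 | −0.59 | +0.12 |
| Early effect | Week 4 | −0.75 | −0.35 |
| Late effect, none at Week 2 | Week 2 | +0.40 | −0.03 |
| Early effect | Week 8 | +0.01 | −0.01 |

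Standard errors at Weeks 2 and 4 are about 3.5–4.6 points. Over all checks, Week 8 S-IGA moves by at most about 0.05 points. Under a global null there was no bias.

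**3. Weekly itch.** Table 3 gives Week 1 six days (2–7), and 6.1.7 requires four scores. With independent daily completion p, a missing Week 1 average has probability P(Bin(6,p) ≤ 3), and a 7-day week P(Bin(7,p) ≤ 3).

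| p | Week 1 | 7-day week |
|---|---|---|
| 0.80 | 0.099 | 0.033 |
| 0.85 | 0.047 | 0.012 |
| 0.90 | 0.016 | 0.003 |

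The Week 1 filled-value ratio is 0.51–1.60, so the effect changes by −5% to +6% at 10% gaps and half that at 5%. SI-NRS Success at Weeks 2 and 4, if imputed, moves by −0.3 to 0 points at 10%. At the 3.3% diary rate that scales to about 0.3 × 0.33 = 0.1 point.

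**4. Week 2 null with a later effect.** The spurious Week 2 effect is 0.012–0.015 SD at 5% gaps and 0.023–0.030 SD at 10% (20,000 trials per scenario). Two-sided rejection at 0.01 stays at 0.008–0.012. Rejection in favour of active is 0.006–0.007 at 5% gaps and 0.007–0.011 at 10%, against 0.005.

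**5. Nested draws.** Let B be the variance between Step 1 draws. With 15 identical copies of each, the single-level rule gives (15 × 9/149)B = 0.906B, and × (1 + 1/150) = 0.912B. The correct component is (1 + 1/10)B = 1.10B. With B at 0.039–0.046 of the within-imputation variance (5% gaps), the SE ratio √[(1 + 0.912b)/(1 + 1.10b)] is 0.996. At 0.078–0.089 (10% gaps) it is 0.992–0.993.

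**6. When a decision would change.** With a 5% loss in z, the corrected p must lie between 0.0067 and 0.010 at α = 0.01 (2.576/0.95 = 2.711), or between 0.0009 and 0.0017 at the first Holm step, 0.01/6 (3.144/0.95 = 3.309).

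**The case against.** The strongest reply concerns size and use. The SAP calls the gaps small, and the 5–10% rates are assumed. For 7-day itch weeks, 10% is three times the highest rate the diary arithmetic supports, and Week 1 reaches it only at 80% daily completion. The largest S-IGA case leaves p far below any threshold, and two-sided error is not visibly inflated. The calculations use unstratified risk differences and mean scores, not the stratified CMH odds ratio with Wilson–Hilferty p-values. Observed-data analyses, plus non-responder analyses for binary endpoints, already bypass Step 1 (8.2, Table 5). A corrected run that does not govern decisions adds only more post-unblinding output.

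Most of this stands as a limit on size. The last two points do not remove the need for the rerun. For the continuous endpoints, Table 5 plans only an observed-data check. Observed-case analyses also exclude subjects who discontinued for adverse events or lack of efficacy, whom the imputed analysis counts as non-responders or sets to baseline (6.1.7). The planned checks change several things at once and cannot isolate Step 1.

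**Conclusion.** The concern holds. The Step 1 model omits treatment in both prose and code, and the nested draws are pooled by a rule meant for independent imputations. Both are errors as written, and both are small.

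At gap rates of 5–10%, the early effects shift by a few percent in either direction and standard errors are understated by less than 1%. At 2% the shift is negligible. The co-primaries and Family 2 are essentially unaffected.

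These sizes rest on assumed gap rates, correlations and time courses, and on statistics simpler than the stratified CMH. Whether SI-NRS Success at Weeks 2 and 4 is exposed depends on which of the conflicting SAP statements applies. The point should be addressed because the affected endpoints are formally tested and the correction is cheap.

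**What to change.** - Run Step 1 BY treatment, or add a 0/1 treatment variable to its VAR list.
- Use 150 Step 1 draws with one Step 2 draw each, or keep 10 × 15 and apply a nested combining rule.
- SAP V3.0 post-dates unblinding (version history; Section 1). Document the change and state before the rerun that the imputation as written governs every Family 1 and Family 3 decision. Report the corrected run as a labelled sensitivity analysis for the exposed endpoints.
- State whether the nonresponse sentence in 6.1.4.1.1, or 6.1.7 with Table 5, applies to SI-NRS Success.
- Report the number of values filled in Step 1 by endpoint, visit and arm, which replaces the assumed gap rate with a fact.

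The cost is one rerun, one documented SAP or CSR entry and one further set of tables. The rerun leaves a separate small error from rounding normal draws for S-IGA (−0.13 to +0.11 points at 10% gaps), which is not part of this point.

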  tables <pooled site group> * <BL S-IGA randomization strata> * <BL B-IGA
randomization strata> * <treatment>
    * <outcome> / cmh commonriskdiff(cl=MH) alpha=0.025;
  output out=example_stat cmh;
run;
```

In order to apply PROC MIANALYZE for the categorical outcomes, normalizing transformations have to be applied to odds ratio. *P* values are obtained using Wilson Hilferty transformation as illustrated by Ratitch et.al.⁴

- For continuous outcomes, this step involves running an ANCOVA with terms for the baseline outcome, pooled site group, baseline S-IGA category, and baseline B-IGA category as covariates for each of the completed dataset and combining the results using PROC MIANALYZE

```
proc mixed data=example;
  by <imputationnumber> <visit> ;
  class <pooled site group> <BL S-IGA randomization strata> <BL B-IGA
randomization strata> <treatment>;
  model <outcome> = <pooled site group> <BL S-IGA randomization strata> <BL
B-IGA randomization strata>
    <treatment> <base> / alpha=0.025;
```

```
lsmeans <treatment> / alpha=0.025 pdiff cl;
ods output lsmeans=lsmeans
      diffss=diffss;
run;

*Combines the LS means across the MI datasets;
proc sort data=lsmeans;
  by <treatment> <imputationnumber>;
run;

proc mianalyze data=lsmeans;
  by <treatment>;
  modeleffects estimate;
  stderr stderr;
run;

*Combines the LS mean differences across the MI datasets;
proc sort data=diffss;
  by <treatment> <imputationnumber>;
run;

proc mianalyze data=diffss;
  by <treatment>;
  modeleffects estimate;
  stderr stderr;
run;
```

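### The ANCOVA pooling pseudo code in SAP 6.1.4.1.1 leaves visit out of PROC MIANALYZE, so with multi-visit input it would combine visits as well as imputations

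*SAP*

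**What the plan says.** SAP 6.1.4.1.1 builds the completed datasets in two stages: "Total of 10 imputations are done in the MCMC step", and then "This process will be repeated 15 times, resulting in a total of 150 complete analysis datasets". Its Step 3 code is introduced with "The SAS pseudo code for the multiple imputation process is listed below".

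For continuous outcomes, PROC MIXED runs "by <imputationnumber> <visit>" and writes its LS means and treatment differences to two datasets. Each dataset is sorted "by <treatment> <imputationnumber>" and passed to PROC MIANALYZE, which runs "by <treatment>" with "modeleffects estimate" and the matching standard error. The comment above the second block reads "Combines the LS mean differences across the MI datasets". Visit appears in neither sort nor in either pooling step, and no statement restricts the data to one visit.

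The prose of Step 3 says the ANCOVA results are combined into a single inference and does not mention visit.

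**The concern.** PROC MIANALYZE, used this way, counts each row in a BY group as one imputation. If rows from several visits share a BY group, the point estimate becomes the mean over visits, and real differences between visits are booked as between-imputation variance. Estimate, standard error and p-value then belong to no endpoint in the plan.

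The alpha-controlled continuous endpoints in SAP 6.1.3 are each tied to one timepoint. PSD aggregate change at Week 8 is third of seven in the fixed sequence of Family 2, at 0.005. A wrong p-value there could close, or wrongly open, the four tests after it and the transfer of 0.005 to Family 1. SI-NRS change at Week 1 is fourth of five in Family 1. PASI change at Week 2 is one of six Holm-tested endpoints in Family 3.

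**Working it through.** **The plan's own count.** 10 MCMC imputations × 15 PMM imputations = 150 completed datasets, as stated.

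**Rows per pooling group as listed.** PROC MIXED gives one row per imputation, visit and treatment. Grouping by treatment alone leaves:
- Weeks 2, 4 and 8 (PASI, PSSI, PSD): 150 × 3 = 450 rows.
- Weekly SI-NRS, Weeks 1 to 8 (SAP Table 3): 150 × 8 = 1,200 rows.

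With visit in the BY statements, each group has 150 rows, matching the stated total.

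**Is more than one visit present?** SAP Tables 5 and 6 together send PASI change at Weeks 2, 4 and 8, PSD aggregate change at Weeks 2, 4 and 8, and SI-NRS change at Weeks 1 to 8 through multiple imputation and ANCOVA. Planned tables 14.2.3.4, 14.2.5.4 and 14.2.7.1.1 report these by study visit. The visit term in the PROC MIXED BY statement would be redundant if only one visit were supplied.

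**Rubin's rules.** Over m rows, the estimate is the mean of the row estimates; W is the mean squared standard error; B is the variance of the row estimates; T = W + (1 + 1/m)B; the pooled SE is √T.

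**Worked case (all inputs assumed).** Differences −2.0, −3.0 and −3.5 at Weeks 2, 4 and 8, SE 0.35 each, no imputation-to-imputation variation within a visit.
- Mean = −8.5/3 = −2.83.
- W = 0.35² = 0.1225.
- B = 150 × (0.833² + 0.167² + 0.667²)/449 = 150 × 1.167/449 = 0.390.
- T = 0.1225 + (1 + 1/450) × 0.390 = 0.513, so SE = 0.72 and z = −4.0.
- By visit, Week 2 is −2.0/0.35 = −5.7 and Week 8 is −3.5/0.35 = −10.

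The listed code would overstate a Week 2 effect by 0.83/2.0 = 42% and understate a Week 8 effect by 0.67/3.5 = 19%, with about twice the SE in both cases.

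**Range (all inputs assumed).** The rows below were simulated with 150 imputations per visit and a between-imputation SD of 0.08 within each visit.

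| Differences, Weeks 2/4/8 | SE | Week 2 alone, p | Week 8 alone, p | As listed: estimate, SE, p |
|---|---|---|---|---|
| −2.0/−2.0/−2.0 | 0.3 | 7.6e-11 | 9.6e-11 | −2.0, 0.31, 8.5e-11 |
| −2.0/−2.0/−2.0 | 0.5 | 8.0e-5 | 7.8e-5 | −2.0, 0.51, 7.8e-5 |
| −1.0/−1.5/−2.0 | 0.3 | 0.0012 | 1.5e-10 | −1.5, 0.51, 0.0033 |
| −1.0/−1.5/−2.0 | 0.5 | 0.047 | 8.0e-5 | −1.5, 0.65, 0.021 |
| −0.8/−2.0/−3.2 | 0.3 | 0.011 | 1.1e-24 | −2.0, 1.04, 0.054 |
| −0.8/−2.0/−3.2 | 0.5 | 0.11 | 2.5e-10 | −2.0, 1.10, 0.071 |
| 0/−1.5/−3.0 | 0.3 | 0.99 | 4.9e-22 | −1.5, 1.26, 0.24 |

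Against 0.025, the highest level any secondary test can reach, a Week 2 endpoint moves from 0.047 to 0.021 in the fourth row and from 0.011 to 0.054 in the fifth. A Week 8 endpoint tested at 0.005 would be lost in the last four rows although its own p-value is at most 8.0e-5. With equal effects at all visits almost nothing changes.

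**The case against.** The listing is labelled pseudo code, uses placeholders and could not be run literally in any case. Step 2 writes to one dataset name while Step 3 reads the Step 1 input. Step 1 rounds to integers although the text exempts PASI and the itch scales. The reshaping and the pooling of the CMH results are not shown. The intent is also plain: the comments speak of combining across imputed datasets, the total is fixed at 150, the endpoints are single-timepoint, the planned tables are by visit, and the ANCOVA code for non-imputed data in SAP Section 8 runs by visit. A programmer would probably notice one result line where a table needs three. If the data were limited to one visit beforehand, the code would be correct.

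All of this stands, and it limits the weight of the point. It does not remove it. The listing is the only place that states the grouping for pooling, the prose is silent on visit, and no single-visit restriction is written.

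A reader might infer that the trial's continuous secondary results are wrong, or that the co-primary results are. The documents support neither. They contain no production program and no estimates. S-IGA and B-IGA success are analysed by CMH, for which no PROC MIANALYZE code is shown. Nor does the slip always exaggerate the effect; the table shows it can go either way.

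**Conclusion.** The pooling specification is wrong as written whenever the input holds more than one visit, and it conflicts with the SAP's own single-timepoint endpoints, dataset count and by-visit tables. It concerns the multiply imputed ANCOVA endpoints only. The row counts, 450 or up to 1,200 instead of 150, follow from the SAP. The effect on estimates and p-values cannot be sized from the documents. The ranges above rest entirely on assumed treatment differences and standard errors, and show anything from no material change to a changed test decision in either direction. This is a specification error with clear intent and a trivial correction, worth fixing because some of the affected tests gate others in the alpha-controlled sequence.

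**What to change.** Put `<visit>` first in both PROC SORT BY statements (visit, treatment, imputation number) and in both PROC MIANALYZE BY statements (visit, treatment). For the daily SI-NRS endpoints at 72 hours and Day 1, use study day in the same role.

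SAP Version 3.0 was written after database lock and unblinding, so the sponsor should also confirm that the production program pooled 150 rows per visit and treatment for LS means, and 150 per visit for the treatment difference, and record this in the clinical study report.

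The cost is four edited lines and one log check. No data, method or alpha allocation changes.
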